6.2 Serious Adverse Events

The Investigator is responsible for recognizing and reporting SAEs as outlined in this section. It is the Sponsor or designee's responsibility to report relevant SAEs to the applicable local, national, or international regulatory bodies.

6.2.1 ***Definitions of Serious Adverse Events***

An SAE is defined as any untoward medical occurrence that:

- results in death
- is immediately life-threatening
- requires at least a 24-hour inpatient hospitalization or prolongation of existing hospitalization
- results in persistent or significant disability/incapacity
- is a congenital anomaly/birth defect.

The definition of SAE also includes any important medical event. Medical and scientific judgment should be exercised in deciding whether expedited reporting is appropriate in other situations, such as important medical events that may not be immediately life-threatening or result in death or hospitalization, but may jeopardize the subject or may require intervention to prevent one of the other outcomes listed in the previous definition. These should also usually be considered serious. Examples of such events are intensive treatment in an emergency room or at home for allergic bronchospasm; blood dyscrasias, or convulsions that do not result in hospitalization; or development of drug dependency or drug abuse.

“Disease progression” or “relapse from remission” as such, should not be reported as an SAE.

Treatment within or admission to the following facilities is not considered to meet the criteria of “inpatient hospitalization” (although if any other SAE criteria are met, the event must still be treated as an SAE and immediately reported):

- Emergency Department or Emergency Room
- Outpatient or same-day surgery units
- Observation or short-stay unit
- Rehabilitation facility
- Hospice or skilled nursing facility
- Nursing homes, Custodial care or Respite care facility

Hospitalization during the study for a pre-planned surgical or medical procedure (one which was planned prior to entry in the study), does not require reporting as an SAE.

6.2.2 *Serious Adverse Event Reporting by Investigators*

It is important to distinguish between “serious” and “severe” AEs, as the terms are not synonymous. Severity is a measure of intensity; however, an AE of severe intensity need not necessarily be considered serious. For example, nausea which persists for several hours may be considered severe nausea but may not be considered an SAE. On the other hand, a stroke which results in only a limited degree of disability may be considered only a mild stroke but would be considered an SAE. Severity and seriousness should be independently assessed when recording AEs and SAEs.

Adverse events classified by the treating Investigator as serious require expeditious handling and reporting in order to comply with regulatory requirements. Serious AEs may occur at any time from the start of study treatment through the 30-day follow-up period after the last study treatment. All SAEs, regardless of causality, must be reported within 24 hours of when the Investigator is first informed of the event and followed until resolution (with autopsy report, if applicable). Serious AEs that occur prior to assignment of study treatment, that are related to a protocol-mandated intervention, including invasive procedures such as biopsies, are to be reported.

All SAEs, regardless of causality, must be entered in the eCRF and supporting documentation (i.e., hospital records, autopsy reports) must be reported to:

Clinipace Worldwide
[contact]
Email: [contact]

MEI Pharma – Medical Monitor
Phone: primary ([name]): [contact];
back-up ([name]): [contact]

Deaths and other SAEs occurring > 30 calendar days after last study treatment that are deemed related (causality = YES) to pracinostat must be reported as SAEs within 24 hours of when the Investigator is first informed of the event. Whenever possible, an autopsy report should be collected.

Deaths occurring > 30 calendar days after last study treatment and not attributed to study treatment (e.g., disease progression) need not be reported as SAEs, but should be collected as part of the study data.

Follow-up information for SAEs and information on non-serious AEs that become serious should also be reported as soon as it is available. Refer to the study reference manual for detailed SAE reporting guidelines.

Investigators must report SAEs and follow-up information to their responsible IRB/EC according to its policies.

6.2.3 *Sponsor Serious Adverse Event Reporting Requirements*

The Sponsor or designee is responsible for reporting relevant SAEs to the competent authority, other applicable regulatory authorities, and participating Investigators, in accordance with the International Council on Harmonisation (ICH) guidelines, FDA regulations, and/or local regulatory requirements.

6.3 Recording of Adverse Events and Serious Adverse Events

6.3.1 *Diagnosis versus Signs and Symptoms*

All AEs should be recorded individually unless the AEs constitute components of a recognized condition, disease, or syndrome. If a constellation of signs and/or symptoms cannot be medically characterized as a single diagnosis or syndrome at the time of reporting, each individual event should be recorded as an AE or SAE as appropriate. If a diagnosis is subsequently established, it should be reported as follow-up information is available. If a diagnosis is determined subsequent to the reporting of the constellation of symptoms, the signs/symptoms should be updated to reflect the diagnosis.

6.3.2 *Persistent or Recurrent Adverse Events*

A persistent AE is one that extends continuously, without resolution, between subject evaluation time points. Such events should only be recorded once. If a persistent AE becomes more severe or lessens in severity, it should be recorded separately.

A recurrent AE is one that occurs and resolves between subject evaluation time points, and subsequently recurs. All recurrent AEs should be recorded.

6.3.3 *Abnormal Laboratory Values*

If an abnormal laboratory value or vital sign is associated with clinical signs and/or symptoms, the sign or symptom should be reported as an AE or SAE, and the associated laboratory value or vital sign should be considered additional information that must be collected. If the laboratory abnormality is a sign of a disease or syndrome, only the diagnosis should be recorded.

Abnormal laboratory values will be reported as an AE if the laboratory result requires an adjustment in the study medication(s) or discontinuation of treatment; and/ or laboratory findings require additional testing or surgical intervention; a laboratory result or finding is associated with accompanying symptoms; or a laboratory result is considered to be an AE by the Investigator.

6.3.4 *Deaths*

Deaths that occur during the protocol-specified AE reporting period that are attributed by the Investigator solely to progression of disease should be recorded in the Death Report CRF.

All other on-study deaths, regardless of attribution, will be recorded as an SAE and expeditiously reported.

When recording an SAE with an outcome of death, the event or condition that caused or contributed to the fatal outcome should be recorded as the single medical concept.

6.3.5 *Hospitalization, Prolonged Hospitalization, or Surgery*

Any AE that results in hospitalization of > 24 hours or prolongation of preexisting hospitalization should be documented and reported as an SAE unless specifically instructed otherwise in this protocol. There are some hospitalizations that do not require reporting as an SAE (see [Section 6.2.1](#)).

6.3.6 *Preexisting Medical Condition*

A preexisting medical condition is one that is present at the start of the study. Such conditions should be recorded as part of the subject's medical history. A preexisting medical condition should be recorded as an AE or SAE only if the frequency, severity, or character of the condition worsens during the study. When recording such events, it is important to convey the concept that the preexisting condition has changed by including applicable descriptors.

6.3.7 *New Cancers*

The development of a new primary cancer should be regarded as an AE and will generally meet at least one of the serious criteria (see [Section 6.2.1](#)). New primary cancers are those that are not the primary reason for the administration of the study treatment and have developed after the inclusion of the subject into the study. They do not include metastases of the original cancer. Symptoms of metastasis or the metastasis itself should not be reported as an AE/SAE, as they are considered disease progression.

6.4 Adverse Events of Special Interest

Adverse Events of special interest (AESI) are defined as pre-specified AEs, serious and non-serious, under ongoing monitoring by the Sponsor. No specific reporting timelines or other activities are required by the Investigator in addition to the normal AE reporting practices as described in the above sections for the following AESIs:

- Supraventricular arrhythmias
- Sepsis, septic shock, Grade ≥ 3 lung infection (pneumonia)
- Any infection leading to death
- Grade ≥ 3 anemia, neutropenia, febrile neutropenia, and thrombocytopenia
- Grade ≥ 3 hemorrhage

6.4.1 QTc Prolongation

Any QTc prolongation \geq 500 ms and/or $>$ 60 ms change from baseline, irrespective of the relationship to study treatment, must be always reported as an AE (see [Section 6.1.2](#)).

The Investigator or the Investigator's designee must complete the AE pages of the eCRF with all necessary information, and any accompanying source documents (hospital records, ECG report, etc.) should be faxed or e-mailed (as PDFs) at the following contacts:

Clinipace Worldwide
[contact]
Email: [contact]

6.4.2 Pregnancy, Abortion, Birth Defects/Congenital Anomalies

Female subjects of child-bearing potential and male subjects (even if surgically sterilized) must:

- Agree to practice effective barrier contraception during the entire study treatment period and for 30 days following last dose, or
- Agree to completely abstain from heterosexual intercourse.
- Male subjects must also refrain from donating sperm during their participation in this study.

During the course of the study, all female subjects of childbearing potential (the definitions of "women of childbearing potential" are listed in [Appendix G](#)) must contact the treating Investigator immediately if they suspect that they may be pregnant (a missed or late menstrual period should be reported to the treating Investigator).

If an Investigator suspects that a subject may be pregnant after the subject has been receiving study medications, study drugs must immediately be withheld until the result of the pregnancy test is confirmed. If a pregnancy is confirmed, study drugs must be immediately and permanently stopped, the subject must be discontinued from the study, and the Investigator must notify the Sponsor/designee as soon as possible.

If a subject becomes pregnant while enrolled in the study, the Investigator should expeditiously report this event, regardless of whether or not it meets the criteria for expedited reporting. Abortions (spontaneous, accidental, or therapeutic) must also be reported. Refer to [Appendix G](#) for detailed information on the pregnancy reporting process.

6.4.3 Pracinostat Overdose

There is no specific antidote to pracinostat. If overdose is suspected, administration of study drug should be stopped, and general supportive measures instituted. The risk of overdose is minimized by the standard dose and written dosing instructions for subjects.

Symptomatic and non-symptomatic overdose (e.g., $>$ 45 mg single dose or $>$ 2 doses in a $<$ 48-hour interval) must be collected as part of the study data. Any accidental or intentional

overdose with the study drug that is symptomatic, even if not fulfilling a seriousness criterion, is to be reported within 24 hours from first knowledge of the event and following the same process described for SAE reporting (see [Section 6.2.2](#)).

6.5 Study Drug Dose Modifications

Adverse events and laboratory abnormalities (see [Appendix A](#) for details) will be monitored throughout the study and toxicities will be graded per NCI CTCAE v4.03. Appropriate supportive care treatment, such as antiemetics or antidiarrheal treatment, will be administered according to local standards of care as appropriate, prior to considering study drug dose modification or interruption.

If necessary to manage toxicities, azacitidine dose reduction will be implemented according to its package insert or local standards of care. Pracinostat dose reduction to less than 45 mg is not planned in this study. Of note, there may be overlapping toxicities between azacitidine and pracinostat, particularly for myelosuppression, fatigue, nausea, and vomiting.

6.5.1 *Dose Modification or Interruption for Non-Hematologic Toxicity*

From Cycle 2 onwards in case of Grade ≥ 3 non-hematologic toxicities a dose reduction or, as a subsequent option, a dose interruption of both pracinostat and azacitidine is permitted after prior discussion with the Medical Monitor.

Patients with Grade ≥ 3 non-hematologic toxicities may have both study drugs held up to a maximum of 4 weeks, or until return to Grade 1 or baseline (whichever comes first). However, in patients who are experiencing a reduction in marrow blasts but have not achieved counts $< 5\%$, dose interruptions beyond 28 days are permitted, but require prior discussion with the Medical Monitor.

- If unexplained reductions in serum bicarbonate levels (or CO₂ if bicarbonate is not routinely measured at the site) to < 20 mmol/L occur, then the azacitidine dose should be reduced by 50% for all subsequent cycles.
- If unexplained elevations of urea/BUN or serum creatinine to ≥ 2 -fold above baseline values and above ULN occur, then the next cycle should be delayed until values return to normal or baseline, and the azacitidine dose should be reduced by 50% for all subsequent cycles.
- When a QT prolongation is observed for the first time, the patient should be followed with additional ECGs as determined by the Investigator. All study drugs should be held until QT returns to baseline in patients who develop any of the following, unless there is a clear alternative cause for the changes:
 - Sustained (at least two ECG measurements, approximately 30 minutes apart) QTcF that is ≥ 500 ms and/or > 60 ms longer than the baseline value.
 - New ECG finding of clinical concern.

Study drugs may be resumed, provided that any ECG abnormalities have been resolved, and underlying causes have been addressed, the patient remains clinically stable and is appropriately monitored. Clinical judgment should be applied.

6.5.2 Dosage Adjustments of Study Drugs

Subjects will receive one course of therapy during every 28-day cycle. The Medical Monitor will review with the Investigator any decision to reduce or discontinue either of the study drugs (pracinostat or azacitidine).

In the presence of toxicity, azacitidine dose reduction must be implemented according to its package insert or local standards of care. Azacitidine dose reduction is not allowed in Cycle 1 but may be implemented in Cycle 2, if deemed clinically necessary.

If after Cycle 4 the subject experiences continued toxicity despite azacitidine dose reduction, then the schedule of pracinostat administration may be reduced as presented in Table 1. Please discuss with the Medical Monitor before reducing the dose of pracinostat from 3 to 2 weeks per cycle.

Table 1 Pracinostat Dose Level Modifications

Dose Level	Pracinostat
Starting Dose	45 mg administered orally once a day, 3 days each week (e.g., Monday, Wednesday, Friday) for 3 consecutive weeks, followed by 1 week of rest, in 28-day cycles
Dose Level -1	45 mg administered orally once a day, 3 days each week (e.g., Monday, Wednesday, Friday) for 2 consecutive weeks , followed by 2 weeks of rest, in 28-day cycles

7 STUDY DRUG

7.1 Study Drug

Investigational Product	Dosage Form and Strength
Pracinostat	45-mg capsules

7.1.1 Study Drug Labeling, Packaging, and Supply

Pracinostat 45-mg capsules will be supplied by MEI Pharma.

All study drugs must be kept in a secure place under appropriate storage conditions. Pracinostat capsules should be stored at controlled room temperature, 20 – 25°C (68 – 77°F) with excursions allowed between 15 – 30°C (59 – 86°F).

7.1.2 Preparation and Administration of Study Drug

No preparation of pracinostat is necessary.

Details of pracinostat administration are provided in [Section 3.1.1](#).

7.1.3 Accountability of Study Drug

The Investigator (or designee) is responsible for accountability of all used and unused study medication supplies at the site.

The Sponsor or its representatives must be granted access on reasonable request to check drug storage, dispensing procedures, and accountability records.

All study drug inventories must be made available for inspection by the monitor, the Sponsor (or its designees), and regulatory agency inspectors upon request.

At the end of the study, study drug will be returned to the Sponsor (or designee) or destroyed. Study drug must not be destroyed unless prior approval has been granted by the Sponsor or its representative.

7.1.4 Precautions and Risks Associated with the Study Drug

Precautions and associated risks with pracinostat	
Hematologic	Treatment with pracinostat has been associated with cytopenias including anemia, thrombocytopenia, and neutropenia. The incidence of cytopenias may increase with increasing doses of pracinostat. Subjects participating in clinical studies of pracinostat should be monitored closely for adverse hematologic affects. The effect of dose reduction on the amelioration of cytopenias has not been established, however prudent clinical management, including supportive care (appropriate use of transfusions and/or hematopoietic growth factors) and dose modification or discontinuation should be followed (see Section 6.5).
Gastrointestinal	Gastrointestinal disturbances (including nausea, vomiting, and diarrhea) have been reported in subjects treated with pracinostat. Standard antiemetic and antidiarrheal medications and appropriate supportive care should be used per normal clinical practice in subjects participating in clinical studies of pracinostat. Preexisting nausea, vomiting, and diarrhea should be adequately controlled before beginning therapy.
QTc Prolongation/Cardiac	Asymptomatic QTc interval prolongation has been observed during clinical studies of pracinostat. Subjects with a CTCAE Grade 2 prolonged QTc interval during screening will not be permitted to participate in clinical studies of pracinostat. Hypokalemia or hypomagnesemia should be corrected prior to pracinostat administration and consideration should be given to monitoring potassium and magnesium in symptomatic subjects (e.g., subjects with nausea, vomiting, diarrhea, fluid imbalance, or cardiac symptoms). See the Investigator's Brochure for additional information on QTc prolongation. Concomitant medications with a known risk of prolonging the QT interval and/or causing Torsades de Pointes are prohibited. In addition, caution should be taken when using concomitant medications with a possible or conditional risk of prolonging the QT interval and/or causing Torsades de Pointes; medications with a possible or conditional risk may be used at the discretion of the Investigator (Appendix H).

Precautions and associated risks with pracinostat	
General Signs and Symptoms	Fatigue has been the most common AE reported in subjects receiving pracinostat and has frequently prompted dose reduction in subjects receiving > 60 mg/day. Anorexia has also been commonly reported. Subjects experiencing debilitating fatigue or anorexia with weight loss may benefit from dose reduction or interruption of pracinostat treatment. Related SAEs of febrile neutropenia, fatigue, and pneumonia have been reported. Disturbances of the GI tract, including nausea, vomiting, and diarrhea, have been reported in patients treated with pracinostat. In the Phase II study of pracinostat + azacitidine in AML, nausea, diarrhea and vomiting were among the most frequently reported manifestations of GI toxicity, with most cases graded as 1 or 2. Standard antiemetic and antidiarrheal medications and appropriate supportive care should be used per normal clinical practice. Pre-existing nausea, vomiting, and diarrhea should be adequately controlled before starting study drug.

Please refer to the IB for detailed information on the risks associated with the use of pracinostat.

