4 SUBJECT POPULATION AND DISCONTINUATION CRITERIA

4.1 Inclusion Criteria

To be eligible for study participation, subjects must meet the following inclusion criteria:

1. Female or male subjects ≥ 18 years-of-age.
2. Histologically or cytologically documented diagnosis of MDS according to the World Health Organization (WHO) classification ([Vardiman 2009](#), [Arber 2016](#); [Appendix B](#)) with $< 20\%$ bone marrow blasts by morphology and a peripheral white blood cell (WBC) count of $< 20,000/\mu\text{L}$.
 - If WBC $\geq 20,000/\mu\text{L}$, cytoreduction with hydroxyurea is permitted prior to enrollment.
 - CMML-1 and CMML-2 subtypes are eligible for study participation.
3. Classified as high or very high risk according to the Revised International Prognostic Scoring System (IPSS-R) risk category ([Appendix C](#)). CMML-1 and CMML-2 subtypes will be considered high-risk MDS and will not require IPSS-R scoring.
4. Bone marrow biopsy (BMBx) and/or aspirate within 28 days prior to planned first study treatment.

5. Clinical indication for treatment with azacitidine.
6. Previously untreated with HMAs (prior therapy with transfusions, hematopoietic growth factors, or immunosuppressive therapy is allowed).
 - Subjects who require start of an HMA (e.g., azacitidine) due to progressing MDS may receive up to 1 cycle of azacitidine within 30 days prior to Cycle 1 Day 1.
7. ECOG performance status of 0, 1, or 2.
8. Adequate organ function as evidenced by:
 - Aspartate aminotransferase (AST) and alanine aminotransferase (ALT) $\leq 2.5 \times$ the upper limit of normal (ULN).
 - Total bilirubin $\leq 1.5 \times$ ULN or total bilirubin of ≤ 2 mg/dL, whichever is higher. Total bilirubin $< 3 \times$ ULN for patients with Gilbert-Meulengracht Syndrome.
 - Serum creatinine $\leq 1.5 \times$ ULN, or creatinine clearance ≥ 40 mL/min according to institutional standards (actual body weight should be used to calculate creatinine clearance).
 - QTcF interval ≤ 450 msec using the mean of triplicate electrocardiograms (ECGs).

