5.1 Screening

The Screening visit should occur \leq 14 days prior to first study treatment. Physical examinations and serum chemistries on Day 1 do not need to be repeated if performed within 7 days prior to Day 1.

The following procedures and assessments will be performed during screening:

- Written informed consent must be obtained prior to initiating any other study-required procedure. Some tests performed prior to obtaining informed consent (e.g., bone marrow biopsy) may not need to be repeated for this study as long as they were performed within the allowed window described in this protocol. This window allows subjects to not unnecessarily repeat tests and impose an undue burden to them.
- Determine eligibility including IPSS-R score for enrollment.
 - Note: IPSS score for subjects enrolled under Amendment 2 will also be calculated for comparison with historical data, however IPSS will not be used to determine eligibility ([Appendix C](#)).
- Medical history, including recent smoking history.
- Transfusion history for 8 weeks prior to first study drug administration.
- Physical examination.
- Vital signs, including height, weight, blood pressure, resting heart rate, and oral temperature.
- ECOG performance status determination (see [Appendix E](#)).
- Baseline signs and symptoms.
- AE/toxicity assessment.
- Concomitant medication review.
- 12-lead ECG in triplicate, approximately once every 2 to 5 minutes to calculate the QTcF interval.
- Two complete blood counts (CBCs) with differential and blasts \geq 7 days apart within 1 month prior to first study drug administration; the second CBC may be obtained on Cycle 1 Day 1 prior to first study drug administration. For this study, a CBC will consist of, at a minimum, WBC count with differential, absolute neutrophil count (ANC), lymphocyte count, red blood cell (RBC) count and indices, hemoglobin, hematocrit, platelets, and blast count where applicable.

- Serum chemistry: glucose, blood urea nitrogen (BUN), creatinine, sodium, potassium, chloride, calcium, carbon dioxide (CO₂), alkaline phosphatase (ALP), AST, ALT, total bilirubin, total protein, albumin, and lactate dehydrogenase (LDH).
- Serum pregnancy test for women of child-bearing potential (must be performed within 7 days of first study treatment).
- Bone marrow biopsy and aspiration within 28 days prior to planned first study treatment.

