5.2 Study Treatment

Study visits should occur on a 28-day schedule. A -4 day to +7-day window is allowable for each clinic visit to accommodate subject request, holidays, weekends, inclement weather, or other unforeseen circumstances.

Pracinostat is to be taken in the morning on an empty stomach or following a light meal once a day on Days 1, 3, and 5 (Week 1); Days 8, 10, and 12 (Week 2); and Days 15, 17, and 19 (Week 3); with a week of rest during Week 4. Pracinostat will be administered in the clinic on Day 1 of Cycle 1, and subjects may self-administer at home on all other days. Pracinostat is to be taken before azacitidine. Missed doses of pracinostat should not be made up (refer to [Section 3.1.1](#)). To monitor pracinostat dosing, subjects will be given a dosing diary card to track medication compliance.

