5.2.1 Day 1, All Cycles

The following procedures and assessments will be performed on Day 1:

- Update of transfusion history for 8 weeks prior to first study drug administration on Cycle 1 Day 1 only
- Physical examination
- Vital signs
- Smoking assessment (for subjects enrolled under Amendment 1)
- ECOG performance status determination
- AE assessment
- Concomitant medication review
- 12-lead ECG performed in triplicate approximately once every 5 to 10 minutes to calculate the QTcF interval. On Day 1 of Cycle 1, ECGs will be obtained pre-dose, pracinostat will be taken, and azacitidine will be administered. Ninety minutes (\pm 15 minutes) post-pracinostat dosing, triplicate ECGs will be repeated. Beyond Cycle 1, non-triplicate ECGs will be performed as clinically indicated.

- Administer pracinostat.
- CBC with differential and blasts.
- Serum chemistry: glucose, BUN, creatinine, sodium, potassium, chloride, calcium, CO₂, ALP, AST, ALT, total bilirubin, total protein, albumin, and LDH.
- Dispense study medication. Following Cycle 1, study medication compliance will be assessed on Day 1 of each cycle.
- Azacitidine administration.
- Response assessments (after Cycle 2 and Cycle 6; see Section 5.2.4).

5.2.2 *Days 2–9, All Cycles*

- AE assessment on each day of azacitidine administration.
- Azacitidine administration (see [Section 3.1.2](#)).

5.2.3 *Day 15 and Day 22 (Cycles 1 and 2 only)*

- Vital signs.
- Smoking assessment (for subjects enrolled under Amendment 1).
- AE assessment.
- Concomitant medication review (Day 22 only).
- CBC with differential and blasts. A manual differential is preferred but is not required at these visits.
- Serum chemistry: glucose, BUN, creatinine, sodium, potassium, chloride, calcium, CO₂, ALP, AST, ALT, total bilirubin, total protein, albumin, and LDH.

5.2.4 *Response Assessments*

To assess hematologic response, CBC with differential including blast cell counts will be obtained every Cycle Day 1 (-4 days to +7 days), and when response assessments and confirmations are scheduled to be performed ([Appendix A](#)).

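### The protocol advises correcting low magnesium before pracinostat, but magnesium is on none of the scheduled chemistry panels

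*Protocol*

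**What the plan says.** The QTc row of Protocol section 7.1.4 advises that "Hypokalemia or hypomagnesemia should be corrected prior to pracinostat administration". The same sentence goes on to say that "consideration should be given to monitoring potassium and magnesium in symptomatic subjects", giving gastrointestinal symptoms, fluid imbalance and cardiac symptoms as examples. The gastrointestinal row adds: "Preexisting nausea, vomiting, and diarrhea should be adequately controlled before beginning therapy".

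The screening panel in section 5.1 begins "Serum chemistry: glucose, blood urea nitrogen (BUN), creatinine, sodium, potassium, chloride, calcium". It continues with carbon dioxide, liver enzymes, bilirubin, proteins and LDH. Section 5.2.1 (Day 1, all cycles) has the same panel: "Serum chemistry: glucose, BUN, creatinine, sodium, potassium, chloride, calcium", and so on. Sections 5.2.3 (Days 15 and 22 of Cycles 1 and 2) and 5.3 (End of Treatment) and Appendix A note h repeat it. Section 5.1 also allows that "Physical examinations and serum chemistries on Day 1 do not need to be repeated if performed within 7 days prior to Day 1".

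Inclusion criterion 8 ("Adequate organ function as evidenced by") covers transaminases, bilirubin, creatinine and QTcF, with no electrolyte limit. Triplicate ECGs are scheduled at screening and, before and 90 minutes after dosing, on Day 1 of Cycle 1. Beyond Cycle 1, ECGs are done only when clinically indicated (section 5.2.1, Appendix A note g).

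**The concern.** The precaution names two electrolytes and the schedule measures one. The advice to correct carries no symptom limit. The advice to monitor does, and it is discretionary. A subject with low magnesium and no symptoms therefore falls under the first half of the sentence, but nothing in the schedule would identify that subject.

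What is at stake is patient safety, specifically QT risk. The same row of section 7.1.4 reports that the QTc prolongation seen so far with pracinostat was asymptomatic. It treats vomiting, diarrhea and fluid imbalance as reasons to look at these electrolytes, and gastrointestinal disturbance is a reported effect of the drug. Section 8.1 permits antiemetics and quinolone prophylaxis. Appendix H lists ondansetron, granisetron and levofloxacin as possible QT risks and ciprofloxacin as a conditional one.

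**Working it through.** The plan states no figure to reproduce. The check compares the texts and then counts what the schedule produces.

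**Where each electrolyte is measured**

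| Place in the protocol | Potassium | Magnesium |
|---|---|---|
| 7.1.4, correct before pracinostat | named | named |
| 7.1.4, consider monitoring if symptomatic | named | named |
| 4.1, criterion 8 | no limit | no limit |
| 5.1, screening panel | measured | not listed |
| 5.2.1, Day 1 of each cycle | measured | not listed |
| 5.2.3, Days 15 and 22, Cycles 1 and 2 | measured | not listed |
| 5.3, End of Treatment | measured | not listed |
| Appendix A note h | measured | not listed |

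In the documents provided, magnesium as an analyte is named only in section 7.1.4.

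**Inputs for the counts**
- Anticipated median participation of about 10 cycles (section 3).
- Pracinostat on 3 days a week for 3 weeks, so 3 × 3 = 9 doses per cycle (section 5.2).
- After Cycle 4, a permitted reduction to 2 weeks, so 3 × 2 = 6 doses per cycle (section 3.1.1, Table 1).
- No dose interruptions (assumption).

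**Doses over 10 cycles**
- Full schedule: 9 × 10 = 90.
- Reduced from Cycle 5: 4 × 9 + 6 × 6 = 72.
- In Cycles 2 to 10, with no scheduled ECG: 90 − 9 = 81, or 72 − 9 = 63.

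**Chemistry draws over 10 cycles**
- Screening plus each Day 1: 1 + 10 = 11, or 10 if Cycle 1 Day 1 is not repeated under the 7-day allowance.
- All scheduled draws: 1 + 10 + 4 (Days 15 and 22 of Cycles 1 and 2) + 1 (End of Treatment) = 16, or 15. The End of Treatment draw follows the last dose and cannot inform correction before dosing.

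**A subject who stops after 3 cycles**
- Doses: 9 × 3 = 27.
- Screening plus Day 1 draws: 1 + 3 = 4, or 3.

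Potassium is measured at every one of these draws. The number of scheduled magnesium values is 0 in each case. The counts show how often a magnesium result could be had without a new needle; they do not measure risk.

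**The case against.** The strongest reply is that the sentence in 7.1.4 reflects a deliberate choice: correct known deficits, and test when symptoms appear. Symptoms are actively sought, with AE assessment on Day 1, on each azacitidine day, and on Days 15 and 22 of Cycles 1 and 2.

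Other QT safeguards are substantial:
- entry QTcF of at most 450 msec on a triplicate mean, and exclusion of unstable arrhythmia requiring treatment;
- a triplicate ECG after the first dose, with clinically indicated ECGs later;
- prohibition of known-risk drugs and caution with possible-risk and conditional-risk drugs;
- AE reporting of marked QTc prolongation (6.4.1) and a hold rule (6.5.1).

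Section 7.1.4 also refers to the Investigator's Brochure for more on QTc. It is not among the documents, so any monitoring advice there could not be checked. All this stands and limits the weight of the point. None of these safeguards in the documents measures magnesium, however, and a symptom trigger does not reach a subject without symptoms.

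A reader might infer more than the documents support:
- **That potassium is also left unreviewed before dosing.** It is drawn at screening and on Day 1 of each cycle, subject to the 7-day allowance, and an instruction to correct low values presupposes that someone looks at them. Only an explicit checklist line is absent.
- **That each cycle's first capsule must wait for the result**, because "Pracinostat will be administered in the clinic on Day 1 of Cycle 1, and subjects may self-administer at home on all other days". Section 3.1.1 has pracinostat taken in the morning and before azacitidine, and its example moves a dose not taken before noon to the next day. A slow result could shift both drugs.
- **That the restart rule in 6.5.1 is deficient.** It already requires underlying causes to be addressed, which covers electrolytes, along with appropriate monitoring and clinical judgment.

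**Conclusion.** The point holds as a minor gap between a precaution and the schedule meant to support it. Low magnesium in a subject without symptoms would not be found by scheduled testing: 0 magnesium values against 72 to 90 scheduled doses over about 10 cycles, or against 27 doses over 3 cycles.

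It is not a breach of a mandatory rule, since 7.1.4 is worded as advice, and it is not evidence of harm. The documents give no rate of hypomagnesemia or of QT events, so the size of the risk cannot be stated. The counts assume no dose interruptions and the anticipated median duration. The sample size and efficacy analyses are unaffected. The right label is a cheap improvement, minor.

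**What to change.** Add magnesium after calcium in the serum chemistry lists for screening and Day 1 of each cycle (sections 5.1 and 5.2.1, and Appendix A note h), so that the correction advised in 7.1.4 can be applied. The 7-day allowance for Day 1 chemistry can stay as it is. Adding magnesium on Days 15 and 22 and at End of Treatment (5.2.3, 5.3) is optional, for consistency; if it is left out there, note h should say which visits include it. Do not add a mandatory hold of the first capsule pending the result, and leave 6.5.1 as worded.

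The cost is one more analyte on blood already drawn (10 to 11 results per subject over 10 cycles) and one CRF field, with no added visit, draw or ECG. The downside is that some mildly low values will prompt replacement or a repeat test. No new SAP analysis is needed: SAP section 10.6 summarizes chemistry by analyte, so magnesium becomes one more analyte in Table 14.3.4.4.
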